#### 4.1.1 Algorithm for Calculating the Primary Implementation Outcome Measure

Two FDA-approved treatments for OUDs that can be provided in medical settings and documented in EHRs are included as OUD treatment. Buprenorphine and injectable XR naltrexone use will be determined from medication orders (EHR data) and procedures (EHR for all health systems and claims data for 2 health systems). Text string searches on generic and brand medication name will be used to ascertain buprenorphine formulations indicated for OUD treatment (sublingual, tablet, film, subdermal implants, and subcutaneous) and injectable XR naltrexone use from medication orders. A clinical co-investigator then reviews all hits on the text string search as part of quality control. Procedure codes will also be used to identify injectable formulations, implants, and oral formulations given in the office setting. Pharmacy dispensings are the gold standard for outpatient non-injectable medication use but they are not comprehensively available for 5 of the 6 health systems (whereas medication orders are routinely available in all 6 health systems). These 4 health systems are not insurers and therefore do not receive claims from outside pharmacies. Site (health system) principal investigators state that patients frequently obtain medications from pharmacies outside of the health system.

A single medication order or procedure code for buprenorphine formulations indicated for OUD treatment or injectable XR naltrexone (the latter with an OUD diagnosis) will be considered OUD treatment, though sensitivity analyses will examine this assumption (Section 5.2.4)

The algorithm for calculating the primary outcome measure of days on OUD medication (buprenorphine or injectable XR naltrexone) is as follows with details in Appendix A.

Ascertained from the EHR and claims as specified above, all buprenorphine and naltrexone XR injections will be quality checked, combined, cleaned and values imputed (as necessary), and collapsed into an episode or episodes (if gaps in use) of OUD treatment.

Episodes of OUD treatment will then be summed to calculate the total patient days covered with OUD treatment in the time-period of interest. Details on estimating episodes of treatment and summing episodes are in Appendix A but briefly they will be estimated as follows from variables

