commonly available in the EHR – medication orders (i.e., medication name, date ordered, form, quantity, strength, strength unit, number of refills, and directions for use [SIG]) and procedures (medication name, form, strength, strength unit, and date administered).

Specifically, we will do the following:

- 1) Perform quality checks for outlier/implausible values for variables required to calculate the outcome and impute outliers/implausible values and missing values. See Appendix A for further details.
- 2) Estimate days' supply for orders of buprenorphine film and sublingual tablets.
  - a. Translate directions for use (SIG) into pills per day (PPD). For example, "Take 1 pill twice a day" is a PPD=2.
  - b. Divide the quantity field by PPD to estimate days' supply. Add any additional day's supply from refills on the original order to estimate the total days' supply of the order. For example, an order with quantity=60, PPD=2, and refills=2 would have a day's supply=90.
- 3) Assign naltrexone injection and buprenorphine subcutaneous Sublocade a day's supply=28.
- 4) Assign Probuphine (implant) a day's supply=180. Assign Brixadi a day's supply of 7 or 28 depending on the product.
- 5) Estimate runout dates (date when the medication supply provided runs out) as order/procedure date plus days' supply. An order (or dispensing in secondary measures for sensitivity analyses) on 1/1/2018 with a day's supply = 15 is estimated to runout on 1/15/2018.
- 6) Prior to dropping injectable XR naltrexone orders or procedures, we will describe patients with both OUD/OD and AUD diagnosis codes and adjudicate if needed
  - a. For patients with 1+ injectable naltrexone orders or procedures and both 2+ OUD/OD and 1+ AUD diagnoses, provide a table of the numbers of OUD/OD and AUD diagnoses in 2 years pre-randomization and a similar table for post-randomization users of naltrexone.
  - b. Adjudicate subjects with both 2+ OUD/OD and 1+ AUD diagnosis codes to decide whether to include or exclude as OUD treatment, using the number of times a code was used from 7a.
  - c. Drop remaining injectable XR naltrexone if OUD diagnosis criteria are not met:
    - i. Drop injectable XR naltrexone in the pre randomization period if there are not 2+ visits with an OUD/opioid overdose (OD) diagnosis (can be 1 OUD and 1 OD code) in the pre randomization period.

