#### **5.2.4.a. Omitting Last Order in an Oral Buprenorphine Treatment Episode**

To address the potential limitations of medication orders, we will conduct sensitivity analyses with the objective 1 main outcome restricted to episodes of treatment with at least two oral buprenorphine orders if the patient has only oral buprenorphine orders (majority of patients), with the last order in the episode omitted in case it was not picked up and taken by the patient. This sensitivity analysis also addresses any short-term buprenorphine therapy to assist with opioid tapers. This does not impact oral buprenorphine captured by procedure codes when given in the office or any injectable buprenorphine, buprenorphine implants, or injectable XR naltrexone. We will also describe the number of treatment days that are excluded in this restrictive analysis by intervention arm and health system. When the last order is omitted, all refills after the last order are also omitted.

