Table 1b. Proportion of buprenorphine orders and unique individuals with data anomalies		
	No. bup orders=	No. subjects=
	n (%)	
Specific cut points		
DD>40		
DD>40 in 3+ consecutive Rx		
DD>40 in < 3 consecutive Rx		
Rxsup<1		
Rxsup>30		
Rxsup >60		
Rxsup>90		
Rxsup>180		
Rxsup=1 & DD>8 mg		
Refills ≥1		
Refills >6		
Rxamt<1		
Rxamt=1		
Rxamt >30		
Rxamt >60		
Rxamt >90		

Table 2b. Distribution of values for raw variables of interest that were imputed					
	Min	25th	50th	75th	Max
Rxamt					
Rxsup					

14) Pull in buprenorphine (J0570, G2070, G2072, Q9991, Q9992, G2068, G2079, G2069, J0571, J0572, J0573, J0574, J057), injectable naltrexone (J2315, G2073, HZ84ZZZ, HZ94ZZZ), and methadone maintenance therapy (HZ91ZZZ, HZ81ZZZ, H0020, G2067, G2078) procedures from procedures data tables and injectable naltrexone (defined as brand= Vivitrol or route=intramuscular) from medication order tables.

Procedure data	Number of occurrences	Unique number of patients
Implant probuphine - J0570, G2070, G2072		
Sublocade - Q9991, Q9992, or G2069		
Oral bup - J0571, J0572, J0573, J0574, or J0575, G2068, G2079		
Oral bup procedure codes after adding up ones billed on same day (see Step 14)		
XR injectable naltrexone procedures (J2315, G2073, HZ84ZZZ, HZ94ZZZ)		
XR injectable naltrexone from medication orders		
Methadone maintenance therapy (HZ91ZZZ, HZ81ZZZ, H0020, G2067, G2078)		

15) Create a start and end date for each bup rx and procedure

- Start date=rxdate (orders) or adate (procedures)
- For bup orders: End date= (rxdate + rxsup) -1
  - If refills, multiply rxsup by number of refills +1 to calculate the end date. For example, an order with one refill and rxsup=30 would be  $30*2 = 60$  days. An order with 2 refills and rxsup=30 would be  $30*3=90$  days.
- For oral bup procedures (J0571, J0572, J0573, J0574, J0575), set rxsup=1 and enddate=(adate + rxsup)-1. Essentially, each procedure code for oral med covers 1 day. If duplicates (same day for any of these 5 codes), add them together and then keep 1. For example, a subject with 3 oral bup codes (any not distinct codes) on 1/1/2020 would have a start date of 1/1/2020 and rxsup=3. Keep just one of these records with rxsup=3 and enddate=(1/1/2020 + 3) -1 or 1/3/2020
- For oral bup procedures (G2068 or G2079), set rxsup=7 and enddate=adate + rxsup -1

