- For procedures J0570, G2070, G2072: (buprenorphine rods; brand is probuphine): enddate=adate+179 days
- For procedure Q9991, Q9992, or G2069 (Sub Q buprenorphine; brand is sublocade): enddate=adate + 27 days
- For injectable naltrexone (from procedure codes J2315, G2073 or naltrexone XR injectable orders (brand=Vivitrol or route=intramuscular): enddate=adate (procedure) or rxdate (order) + 27 days
- Define the list of OUD ICD-9 and ICD-10 diagnosis codes
 

Opioid abuse	F11.1
Opioid abuse, uncomplicated	F11.10
Opioid abuse, in remission	F11.11

Opioid abuse with intoxication	F11.12
Opioid abuse with intoxication, uncomplicated	F11.120
Opioid abuse with intoxication delirium	F11.121
Opioid abuse with intoxication with perceptual disturbance	F11.122
Opioid abuse with intoxication, unspecified	F11.129
Opioid abuse with opioid-induced mood disorder	F11.14
Opioid abuse with opioid-induced psychotic disorder	F11.15
Opioid abuse with opioid-induced psychotic disorder with delusions	F11.150
Opioid abuse with opioid-induced psychotic disorder with hallucinations	F11.151
Opioid abuse with opioid-induced psychotic disorder, unspecified	F11.159
Opioid abuse with opioid-induced disorder	F11.18
Opioid abuse with opioid-induced sexual dysfunction	F11.181
Opioid abuse with opioid-induced sleep disorder	F11.182
Opioid abuse with other opioid-induced disorder	F11.188
Opioid abuse with unspecified opioid-induced disorder	F11.19
Opioid dependence, uncomplicated	F11.20
Opioid dependence, in remission	F11.21
Opioid dependence with intoxication, uncomplicated	F11.220
Opioid dependence with intoxication delirium	F11.221
Opioid dependence with intoxication with perceptual disturbance	F11.222
Opioid dependence with intoxication, unspecified	F11.229
Opioid dependence with withdrawal	F11.23
Opioid dependence with opioid-induced mood disorder	F11.24
Opioid dependence with opioid-induced psychotic disorder with delusions	F11.250
Opioid dependence with opioid-induced psychotic disorder with hallucination	F11.251
Opioid dependence with opioid-induced psychotic disorder, unspecified	F11.259
Opioid dependence with other opioid-induced disorder	F11.28
Opioid dependence with opioid-induced sexual dysfunction	F11.281
Opioid dependence with opioid-induced sleep disorder	F11.282
Opioid dependence with other opioid-induced disorder	F11.288
Opioid dependence with unspecified opioid-induced disorder	F11.29
Opioid type dependence, unspecified	304.00
Opioid type dependence, continuous	304.01

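### For XR-naltrexone the order and the injection each earn 28 days from their own date with no link between them, so one injection given L days after its order counts as 28+L treatment days (for L up to 35)

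*SAP*

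**What the plan says.** SAP Appendix A2 step 14 pulls XR-naltrexone from procedure tables and also pulls "injectable naltrexone (defined as brand= Vivitrol or route=intramuscular) from medication order tables". The step 14 tally has a separate line for "XR injectable naltrexone from medication orders", so both sources enter the algorithm.

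Step 15 sets the start of each record as "Start date=rxdate (orders) or adate (procedures") and the end, for injectable naltrexone, as "enddate=adate (procedure) or rxdate (order) + 27 days". Section 4.1.1 step 3 agrees: "Assign naltrexone injection and buprenorphine subcutaneous Sublocade a day's supply=28".

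Three rules might be expected to remove a second count. None does.

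- **De-duplication** (A2 steps 1 to 3) compares orders with other orders of the same drug, date and strength.
- **Overlap** (Section 4.1.1 step 9 and Appendix A3) counts a shared calendar day once. Days covered by only one of the two records all still count.
- **Linking** (Section 5.2.4.c) ties dispensings to orders within 30 days, in a sensitivity analysis only.

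Gaps of up to 7 uncovered days between records are filled in (Section 4.1.1 step 7). The sensitivity analysis that drops the last order, Section 5.2.4.a, leaves untouched "any injectable buprenorphine, buprenorphine implants, or injectable XR naltrexone".

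**The concern.** An order for one injection and the record of giving it describe the same 28 days of treatment. The algorithm treats them as two exposures. When the injection follows the order by some days, the wait is counted as treated time, because the order's window fills it and the injection's window then runs its full length.

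These days feed the primary clinic-level outcome and its baseline covariate. They also feed secondary measures built on the same count. In SAP Table 2, treatment duration is cut at 30 days, so a patient with a single injection and a 3-day lag (31 days counted) moves from the 1-30 to the 31-90 category.

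A separate question is the order that was never followed by an injection. It counts as treatment, and no planned analysis shows how much of the outcome rests on such orders.

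**Working it through.** **Inputs.** Each XR-naltrexone record covers 28 days inclusive (start date + 27; A2 step 15). The allowed gap is 7 days (Section 4.1.1 step 7). A gap is counted in uncovered days: Appendix A3 Example 1 calls days 17 and 18 a 2-day gap. Overlapping days count once.

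**The SAP's own figure first.** Section 5.2.4.b takes 10-day orders on 1 and 15 January 2019. They cover days 1-10 and 15-24, leaving days 11-14 uncovered, a gap of 4. With a 7-day allowance the total is 10 + 4 + 10 = 24 days; with a 2-day allowance it is 10 + 10 = 20. Both match the SAP.

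**One order, one injection.** Put the order on day 0 and the injection on day L. The order covers days 0 to 27 and the injection covers days L to L+27.

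- L up to 28: the windows overlap or touch, and together cover days 0 to L+27, which is 28 + L days.
- L from 29 to 35: the gap is L - 28, at most 7, so it is filled: 28 + (L - 28) + 28 = 28 + L days.
- L of 36 or more: the gap exceeds 7, giving two episodes: 28 + 28 = 56 days.

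| Lag L (days) | Days counted | Excess over 28 |
|---|---|---|
| 0 | 28 | 0 |
| 3 | 31 | 3 |
| 7 | 35 | 7 |
| 14 | 42 | 14 |
| 21 | 49 | 21 |
| 28 | 56 | 28 |
| 35 | 63 | 35 |
| 36 or more | 56 | 28 |

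The gap analyses in Supplementary Table 5 move the ceiling but do not remove the excess. The maximum is 28 + 2 + 28 = 58 days with a 2-day gap, 61 with 5 days and 66 with 10 days.

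**Regular monthly series.** Take six injections 28 days apart, each ordered L days ahead. The orders cover days 0 to 167 and the injections cover days L to L+167. The union is 168 + L days against a true 168: 175 at L=7 and 203 at L=35. The lag is gained once per series, not once per injection.

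**Order with no injection.** It counts 28 days, or fewer if it is cut off by the period boundary or overlaps other treatment. It counts only if the patient has at least two visits with an OUD or opioid-overdose diagnosis and, where alcohol use disorder is also coded, is kept at adjudication.

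**What cannot be computed.** The documents give no number of XR-naltrexone injections, no distribution of L and no proportion of orders left ungiven. The excess in the primary outcome scales with all three.

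**The case against.** **Counting orders is a declared choice.** Protocol Section 8.1 uses orders so that the outcome is comparable across sites, SAP Section 4.1.1 lets a single order or procedure count, and Appendix A3 takes the prescriber's intent as its perspective. Procedure claims exist at only two systems, so injection orders guard against injections that were not captured. This stands as a reason to keep unlinked orders in the primary outcome. It does not justify the double window. The intent argument is made for oral medicines whose use cannot be seen, and an order for one injection intends 28 days, not 28+L.

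**The appendix may not be exhaustive.** A2 is headed for oral buprenorphine orders, and Section 4.1.1 says records will be checked, combined and cleaned. A programmer might add a link. But step 15 states an explicit rule for naltrexone orders and procedures, and followed as written it gives the wrong count.

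**Other sensitivity analyses may cover it.** A row label in Supplementary Table 5 mentions orders and procedure codes, but the governing text in 5.2.4.a exempts injectables. Section 8.1 speaks of dispensing data only, but points to Section 5.2.4, where dispensings are added to orders. Neither compares an injection order with its administration.

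**It may not matter much.** This stands. Section 5.2.4.a says most patients have only oral buprenorphine orders, the diagnosis filter limits which naltrexone records count, and a same-day order and injection produces no error.

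**The error might be thought to favour the intervention.** A reader might infer this because injections are an item in the nurse care managers' weekly reports. The documents do not support it. More injections would not by themselves mean longer lags or more ungiven orders, and an on-site nurse could shorten both. The same rule applies in both arms and to the baseline covariate.

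**Conclusion.** For XR-naltrexone the written algorithm overstates treatment days by the order-to-injection lag, up to 35 days for an isolated injection, and by 28 days when the lag is longer. In a regular monthly series the overstatement is about one lag in total. An order without an administration adds up to 28 days when the diagnosis criteria are met, and this is never tested. These results rest on the step 15 dates, the 7-day gap counted in uncovered days, and there being no unstated link.

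Two stronger readings go too far. One is that an injection typically counts as 63 days: that needs a lag of exactly 35 days, and no lag is documented. The other is that all long-acting products are affected. The explicit order rule is for naltrexone. Step 15 starts implant and Sublocade procedure cover at administration (for Sublocade, "Sub Q buprenorphine; brand is sublocade): enddate=adate + 27 days"). Sublocade orders may enter, because Section 4.1.1 searches orders for "sublingual, tablet, film, subdermal implants, and subcutaneous" forms and assigns Sublocade 28 days, but the SAP does not settle it.

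The effect on the primary comparison is unknown in size and direction and may be small. The point merits correction because the rule is wrong as stated and cheap to repair.

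**What to change.** In Appendix A2 step 15:

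1. Link each XR-naltrexone order one-to-one to the first administration of the same product, on or after the order date, within a pre-specified window. The SAP's own 30 days for dispensings is a natural choice. Drop the linked order and start the 28 days at the administration date.
2. Apply this identically at baseline and follow-up and in both arms.
3. Keep unlinked orders in the primary outcome at every system, as the orders-based definition intends. Add a row to Supplementary Table 5 that excludes unlinked injectable orders.
4. State whether Sublocade orders enter the algorithm. If they do, apply the same link.

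After the change, a linked injection counts 28 days whatever its lag. In the new sensitivity row an order never given counts 0.

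The cost is a little more programming on data already extracted. Some orders may be linked to the wrong administration. With a 30-day window, an injection given later than that stays unlinked and keeps the excess shown above (for example 31 + 28 = 59 days at L=31), so the window should be fixed in advance and the lags described with the results.

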#### 17) Determine treatment day

- a. Order all of a patient's orders and procedures by start and end dates. This should include rx and procedures 180 days before day 1 of the time period of interest because these may run out into the time period of interest.

- b. For example: Within a period of interest starting on 1/1/20, a bup order occurring on 12/25/20 for 30 days (end date 1/24/20) would contribute 20 treatment days to January.
- c. During time periods of interest, consider it a day “covered” by buprenorphine or injectable naltrexone during the period of interest if there is bup or naltrexone that covers that day based on rx start and end date. Do not double count if >1 bup or naltrexone on the same day.

Estimate begin and stop dates for each continuous episode (continuous defined as a gap  $\leq 7$  days between end of one bup rx and start of the next bup rx;  $\leq 14$  days between bup end and naltrexone start, and  $\leq 7$  days between naltrexone end and bup or naltrexone start) for all the bup and naltrexone in the time period of interest. In other words, the  $\leq 14$  rule may only be applied when the last day before the gap is covered by bup only and the first day after the bup gap is covered by naltrexone only.

- a. Treatment days = sum of all days covered by bup or naltrexone during the period of interest. No overlap or double counting of treatment days is allowed. In other words, a patient can have a max of 365 days covered by treatment in a year.
  - i. Left and right truncate when time period begins and ends
    1. For example: Bup order that covers 12/15/2019 to 1/14/2020 would stop contributing treatment days on 12/31/2019 if the period of interest ends on 12/31/2019.

**Sensitivity analyses (SA):** The above steps will be replicated for

- 1) A SA that only includes episodes with at least 2 buprenorphine orders omitting last order (and any refills on the order) in an oral buprenorphine treatment episode
- 2) A SA that varies the allowable 7-day gap of continuous use to a lower threshold (based on distribution of the gaps; example: 2 days).
- 3) A SA that uses a combination of orders and dispensings at health systems with some or all (one health system) dispensings data.

For each dispensing, if its rxdate is in “the range” of an order date or a refill date, then it is considered to be linked to that order or refill and dropped in calculations; otherwise, this dispensing is considered as not linked to any order and added to the calculation of days covered. The range is defined as dispensed within 30 days after the order/refill’s start date (an order’s start date is the order’s date; a refill’s start date is derived from the original order’s date and days supply).

This calculation will be done after all data cleaning and imputation.

- 1) A SA that adds in procedure codes for methadone maintenance therapy at sites where this data is available
- 2) A SA that combines SA # 3 and #4 at sites with both dispensing and methadone maintenance therapy data.

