#### **5.2.4.b. Vary the Allowable 7-day Gap to Define Continuous Use Episodes**

To address the limitation that we smooth small gaps of  $\leq 7$  day between medication orders and/or procedures to arrive at continuous episodes of OUD medication use, we will vary the allowable  $\leq 7$  day gap to smaller and larger values (e.g., 2 days, 5 days, 10 days based on descriptive data) when estimating the objective 1 main outcome in this sensitivity analysis. For example, the main analysis treats a 10 day order for buprenorphine on 1/1/2019 and a 10 day order for buprenorphine on 1/15/2019 as one continuous episode lasting from 1/1/2019 to 1/24/2019 (24 days) because the gap between when the first order ran out and the second order began is  $< 7$  days. Altering the allowable gap to only 2 days would result in two different episodes (1/1/2019 – 1/10/2019 and 1/15/2019–1/24/2019) that contribute 20 days of treatment.

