### **A3. Combine OUD Treatments of Buprenorphine and Naltrexone**

- 1) Order all OUD treatments by their respective start and runout dates. See Examples below.
- 2) During time periods of interest, consider it a day “covered” by OUD treatment during the period of interest if there is buprenorphine or injectable naltrexone that covers that day based on start and runout dates. Do not double count covered days.
- 3) Estimate start and end dates for each continuous episode (continuous defined as a gap  $\leq 7$  days between runout date of one OUD treatment and start date of the next

treatment OR  $\leq 14$  days between end date of one buprenorphine prescription and start date of naltrexone) based on days covered for all the buprenorphine and naltrexone in the time period of interest.

- 4) Any gaps not meeting these criteria above result in the end of a continuous episode and these gaps between episodes are NOT part of any episode and do not contribute to treatment days. See examples below.
- 5) Pre and post randomization episodes are not allowed to overlap. They will be left and right censored accordingly. For example, a treatment episode of 90 days with 15 days in the post randomization period (includes randomization date) will be split into two episodes with one episode contributing 75 days of treatment pre-randomization and a second episode contributing 15 days of treatment post randomization.
- 6) OUD treatment days = sum of all episodes [(episode end date – episode start date) + 1] in the pre and post randomization periods.

Examples 1-8 below are each a single patient's prescriptions. These examples are shortened to a 20-day period of interest as an example only. Our perspective here is the prescribers' "intent to treat" (i.e., we do not know how or if patients actually took the oral medications but the assumptions we are making are typical of studies that use electronic health data for studying medication treatment and adherence). (Bup=buprenorphine; NTX=naltrexone)

Example 1: Bup	TIME PERIOD OF INTEREST																				
	-1	1	2	3	4	5	6	7	8	9	10	11	12	13	14	15	16	17	18	19	20
Bup1																					
Bup2																					
Bup3																					
Bup4																					
Bup5																					

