Bup 1 covers day 1 (from a rx occurring during -90 days of period of interest as depicted by coverage on -1 day) and ends day 8; Bup 2 starts day 8 and ends day 11; Bup 3 starts day 12 and ends day 15; Bup 4 starts day 15 and ends day 16; Bup 5 starts day 19 and covers day 19 and 20 – may end on day 20 or after period of interest (truncated).

One continuous episode: Day 1 to Day 20. The gap (day 17 and day 18) is 2 days ( $\leq 7$  days) so smooth it to be continuous.

20 of the 20 day time period of interest is covered by treatment.

Example 2: Bup	TIME PERIOD OF INTEREST																			
	1	2	3	4	5	6	7	8	9	10	11	12	13	14	15	16	17	18	19	20
Bup1																				
Bup2																				
Bup3																				
Bup4																				
Bup5																				

Bup 1 covers day 1 and ends day 6; Bup 2 starts day 1 and ends day 11; Bup 3 starts day 6 and ends day 8; Bup 4 starts day 15 and ends day 16; Bup 5 starts day 16 and ends day 19.

One continuous episode: Day 1 to Day 20. The gap is 4 days ( $\leq 7$  days) so smooth it to be continuous.

Example 3: Bup & NTX	TIME PERIOD OF INTEREST																			
	1	2	3	4	5	6	7	8	9	10	11	12	13	14	15	16	17	18	19	20
Bup1																				
NTX1																				

Bup 1 covers day 1 and ends day 4; NTX1 starts day 10 and covers through day 20 (right truncated since end date would be past time period of interest of 20 days).
 
One continuous episode: Day 1 to Day 20. The gaps in treatment (day 5-9) are <math>\leq 14</math> days.
 
20 of the 20 day time period of interest are covered by treatment.
																				

Example 4: Bup & NTX	TIME PERIOD OF INTEREST																			
	1	2	3	4	5	6	7	8	9	10	11	12	13	14	15	16	17	18	19	20
NTX1																				
Bup1																				

NTX1 1 covers day 1 and ends day 9 (left truncated because it must have begun prior to day 1 given inj ntx lasts 28 days); Bup1 starts day 18 and covers though day 20 (likely right truncated) in the period of interest.
 
Two continuous episodes: 1st episode is Day 1 to Day 9. Then there is a gap <math>>7</math> days so a new episode begins. 2nd episode starts day 18 and ends day 20.
 
12 of the 20 day time period of interest are covered by treatment.
																				

Example 5: Bup	TIME PERIOD OF INTEREST																			
	1	2	3	4	5	6	7	8	9	10	11	12	13	14	15	16	17	18	19	20
Bup1																				
Bup2																				

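### The summation line in SAP Appendix A2 step 17 leaves out the bridged gap days that the SAP's own primary-outcome rule counts, and two of the appendix illustrations fail a recount

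*SAP*

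**What the plan says.** The rule for the primary outcome appears in several places in the SAP, and all but one agree.

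- **Section 4.1.1, step 9** adds up the days of each continuous-use episode. Step 7 has already joined orders separated by gaps of up to 7 days, or up to 14 days from buprenorphine to naltrexone. The section refers to Appendix A for details.
- **Appendix A1** also says that episodes are summed, and refers to A3 for how they are built.
- **Section 5.2.4.b** treats two 10-day orders, dated 1/1/2019 and 1/15/2019, as "one continuous episode lasting from 1/1/2019 to 1/24/2019 (24 days") in the main analysis, and as 20 days when the limit is 2 days.
- **Appendix A3, item 6** states "OUD treatment days = sum of all episodes", each episode counting as end date minus start date plus 1. Item 4 excludes only gaps beyond the limit.
- **Appendix A2, step 17** is the exception. Step 17c counts a day "if there is bup or naltrexone that covers that day based on rx start and end date". The next instruction is to "Estimate begin and stop dates for each continuous episode" with the 7/14-day rule. The total is then "Treatment days = sum of all days covered by bup or naltrexone during the period of interest", with no mention of episodes.

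Step 17 also contains an illustration, 17b. It says a 30-day order of 25 December "would contribute 20 treatment days to January". After the sum it lists the sensitivity analyses that repeat these steps, including "A SA that varies the allowable 7-day gap of continuous use to a lower threshold".

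**The concern.** A bridged gap day lies inside no order's start and end dates. Under step 17c it is not covered, so the step 17 sum gives it nothing, while A3 item 6 counts it. A programmer who works through Appendix A2 in order would build the episodes and then not use them.

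Two things are at stake. First, this is the trial's primary outcome, and Protocol Modification #19 has the Data and Statistics Center check and reproduce the code that creates it. Code written literally from step 17 will not match code written from A3. Second, if only order-covered days are summed, the gap limit has no influence on the total. The sensitivity analysis in 5.2.4.b would then return the primary result at every limit and look like evidence of robustness.

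The worked illustrations are the natural test cases for such code, and some of them do not follow the rules they illustrate. One also leaves it unclear how a gap is counted.

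**Working it through.** **Inputs.** Order dates come from SAP 4.1.1 step 7, 5.2.4.b and Appendix A3 Examples 1–8. The end-date rule is Appendix A2 step 15: start date + days' supply − 1.

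**Two counts.**
- *Episode count* (A3 item 6, 4.1.1 step 9): join orders whose gap is within the limit, then sum (end − start + 1), cut at the limits of the period.
- *Literal step 17 count*: the number of distinct days inside any order's start and end dates.

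**The plan's own figure first (5.2.4.b).** The orders cover days 1–10 and 15–24. Days 11–14 are uncovered, a gap of 4.
- Episode count, 7-day limit: 24 − 1 + 1 = 24, as stated. With a 2-day limit: 10 + 10 = 20, as stated.
- Literal step 17 count: 10 + 10 = 20.

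**Varying the gap limit on that record.**

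| Limit (days) | Episode count | Literal step 17 |
|---|---|---|
| 2 | 20 | 20 |
| 5 | 24 | 20 |
| 7 | 24 | 20 |
| 10 | 24 | 20 |

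**Other worked records.**

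| Record | Stated days | Episode count | Literal step 17 |
|---|---|---|---|
| 4.1.1 step 7 | dates only | 36 | 15 + 20 = 35 |
| Example 1 | 20 | 20 | 16 + 2 = 18 |
| Example 2 | no count | 19 | 11 + 5 = 16 |
| Example 3 | 20 | 20 | 4 + 11 = 15 |
| Example 4 | 12 | 12 | 9 + 3 = 12 |
| Example 5 | 17 | 17 | 17 |
| Example 6 | no count | 20 | 4 + 11 = 15 |
| Example 7 | 20 | 20 | 4 + 11 = 15 |
| Example 8 | no count | 20 | 5 + 11 = 16 |

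The episode count reproduces every day count that the SAP states. The literal step 17 count agrees only where there is no gap or the gap exceeds the limit.

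**Step 17b.** By step 15's rule, 25 December + 30 − 1 is 23 January. Seven days fall in December (25–31), which leaves 30 − 7 = 23 in January. The printed end date of 1/24 would give 24. Neither is 20. The order is also printed as 12/25/20 for a period that starts on 1/1/20, so the year should presumably be 2019.

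**Example 2.** The text says "Bup 5 starts day 16 and ends day 19", yet the episode is said to run to day 20. The previous order group ends on day 11 and the next order starts on day 15, so days 12–14 are uncovered. That is 3 days, but the stated gap is 4, which is the date difference 15 − 11. Examples 1, 6 and 8 state gaps of 2, 5 and 4, which are counts of uncovered days.

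**Why the convention matters.** Take 28 days of supply starting on day 1, with the next record five weeks later on day 36. Supply ends on day 28 and days 29–35 are uncovered.
- Uncovered days: 7, within the limit, so bridged: 35 days per cycle.
- Date difference: 36 − 28 = 8, beyond the limit, so not bridged: 28 days per cycle.

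The ratio is 35/28 = 1.25.

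**Illustrative size across a long record.** Assume consecutive orders of equal length, with all gaps short enough to be bridged. The episode count then exceeds the literal count by about mean gap ÷ order length. For mean gaps of 1 to 3 days:
- 28-day orders: 1/28 = 3.6% to 3/28 = 10.7%.
- 7-day orders: 1/7 = 14.3% to 3/7 = 42.9%.

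The order lengths and gaps here are assumptions, not trial data.

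**The case against.** The strongest reply is that the SAP settles the rule. Step 17 does not say that *only* order-covered days count, and it builds the bridged episodes immediately before the sum. Section 4.1.1 and Appendix A1 both describe the total of days covered as the sum of episodes. A3 item 2 repeats the definition in step 17c, and item 6 still sums whole episodes. Example 1 calls all 20 days covered despite a 2-day gap. A sensitivity analysis on the gap limit has a purpose only if bridged days count. Code that omitted them would fail the printed 24-versus-20 example in 5.2.4.b, and independent replication could expose the error.

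Most of this stands. A reader might infer from step 17 that the SAP holds two competing formulas and that the primary outcome is undefined. The documents do not support that reading, since every other statement of the rule points the same way.

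It does not rescue the line itself. By the definition given in the same step, the sum yields a figure that the SAP elsewhere contradicts. Section 4.1.1 sends the programmer to Appendix A for detail, and the sensitivity analyses are told to repeat the appendix steps.

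On Example 2, the shaded grid is not legible in the text available, so it cannot be said whether the wording or the grid is wrong. The wording alone is inconsistent. Examples 1, 3, 6 and 8 point to counting uncovered days, but step 16 describes the gap as lying between an end date and the next start date, which also allows a date difference.

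**Conclusion.** The primary outcome is the sum of continuous-episode lengths with bridged gaps included. The step 17 summation line is an outlier that, read with step 17c, omits those days: 20 instead of 24 in the SAP's own 5.2.4.b record, 18 instead of 20 in Example 1, and 15 instead of 20 in Example 3. Coded that way, the gap-limit sensitivity analysis would have no effect at any limit. Step 17b should give 23 days, not 20. Example 2 contradicts itself as worded. Whether a gap of exactly 7 uncovered days is bridged depends on a convention the SAP illustrates but does not define.

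These counts follow directly from dates printed in the SAP. The percentage ranges do not: they illustrate assumed order lengths and gaps. A reader might go on to infer that the treatment comparison would be biased because one arm uses shorter orders. The documents give no order lengths by arm, so no difference between arms can be claimed.

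This is a defect of specification in one operational line and its illustrations. It should be corrected because the line belongs to the primary-outcome algorithm and the code is meant to be reproduced by others.

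**What to change.** In SAP Appendix A:

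1. Replace the step 17 sum with the A3 item 6 formula: total the value (end − start + 1) over episodes, each truncated to the period of interest.
2. Define a gap once, in step 16, as the number of uncovered days between one end date and the next start date. Examples 1, 6 and 8 already count it this way.
3. Correct step 17b to an end date of 1/23 and 23 January days, and correct the year of the order.
4. Reconcile the text of Example 2 with its grid. As worded, it is an episode of days 1–19 with a 3-day gap.

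The corrected examples and the 5.2.4.b record can then serve as test cases for the primary-outcome code. The cost is appendix wording only. The design, data collection, model and intended outcome definition do not change.
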